5. STUDY TREATMENTS

5.1 Allocation to Treatment (see also 6.4)

Randomization Process: Subjects who meet all Inclusion/Exclusion criteria, including OSA on baseline or clinical PSG, will be randomized (2:1 randomization) to expedited PAP therapy (Group 1, n~93), or standard care PAP therapy (Group 2, n~47), after the subject has signed consent, completed the baseline activities, Randomization will be stratified by sleep apnea severity (RDI < or >=30) to minimize imbalances in apnea severity between groups.

5.2 Blinding

PSG technicians, PSG interpreters, and study staff who conduct and score neuropsychological tests will remain blinded to group allocation for the duration of the study. **The subject, PI, co-investigators, coordinators, and statistician will not be blinded.**

5.3 Treatment with Positive Airway Pressure (PAP) Therapy: Unless already performed at U-M sleep lab within the past year, all subjects who are diagnosed with OSA on baseline or clinical PSG (n~140) will undergo PAP titrations* and be prescribed clinical PAP therapy by clinicians involved in the study or the subject's treating sleep provider. PAP therapy is considered standard clinical care for patients with obstructive sleep apnea. PAP is a mode of respiratory ventilation that blows air into the nose (or nose and mouth) to splint the upper airway open during sleep. PAP therapy can be delivered at a continuous pressure (CPAP), at different levels during inspiration and expiration (BiPAP), or at a range of auto-adjustable levels depending on the patient's breathing (AutoPAP)*. In order to determine which pressure setting most effectively treats an individual's sleep apnea, an overnight PAP titration study is typically required. This study is similar to a PSG in terms of overnight monitoring but also involves fitting of various masks which are then hooked up to the subject and PAP machine to test the effectiveness of various PAP settings, and to determine which mask/setting is most tolerable for the subject. PAP titration studies will be scored by certified PSG technologists and interpreted by a board-certified sleep physician, who will then place an order for PAP equipment at appropriate settings with a local durable medical equipment (DME) provider. DME will be covered by the subject's insurance.

* In some cases, insurance carriers will not cover the cost of an in-laboratory PAP titration, and instead will recommend an “auto-adjusting” PAP machine (also known as AutoPAP, or APAP) so that patients diagnosed with OSA may begin PAP without requiring a PAP titration.

AutoPAP differs from a CPAP in that it uses algorithms to sense subtle changes in the user's breathing and deliver only the amount of pressure necessary to keep the airway open. In cases where AutoPAP is recommended by the participant's insurance carrier and no medical or PSG contraindications to AutoPAP exist, participants will be allowed to waive their in-lab PAP titration and start AutoPAP therapy according to their PAP randomization assignment.

6. STUDY PROCEDURES

6.1 Screening/Baseline Visit

Subjects will be seen at one of several University of Michigan clinical or research study sites for baseline visit activities, including but not limited to the Michigan Clinical Research Unit (MCRU), or the Department of Neuropsychology testing suite in the Med-Inn Building. Inclusion and Exclusion Criteria will be reviewed, and informed consent will be obtained by qualified study staff. Consenting subjects who meet eligibility criteria at screening will be enrolled and receive their baseline evaluation, where they will undergo the following assessments:

- 1) Demographic information
- 2) Focused medical and surgical history as it relates to multiple sclerosis, sleep, and cardiopulmonary history
- 3) Medication review
- 4) Assessments of height, weight, and neck circumference
- 5) Expanded Disability Status Scale self-report questionnaire (a self-reported measure of MS-related disability)
- 6) Pregnancy test (for females of childbearing age)
(if a pregnancy test was performed within the past month, that result may be used and the test does not need to be repeated)
- 7) Fatigue, insomnia, and sleepiness assessments (see 7.2)
- 8) Pain, anxiety, and quality of life assessments (see 7.2)
- 9) Baseline neuropsychological testing (see 6.2)*
- 10) Unless already done clinically at U-M sleep lab within the past year, baseline polysomnography (PSG, see 6.3)

*If subjects are unable to complete baseline neuropsychological testing on the day of their baseline visit, this will be scheduled within 3 weeks of screening/baseline visit.

6.2 Cognitive (Neuropsychological) Testing

The Minimal Assessment of Cognitive Function in MS (MACFIMS)^{26,27} is a validated, 90-minute neuropsychological battery comprised of a collection of standardized cognitive tests

which assess 5 main cognitive domains that are commonly affected in MS: processing speed/working memory, learning, executive function, visual-spatial processing, and language function, using 7 standard measures. Endorsed by the Consortium of Multiple Sclerosis Specialists (CMSC), it is one of the most accepted neuropsychological batteries in the field. All MACFIMS testing will be performed by blinded, trained psychometricians who are part of the pool of technicians in the department of Psychiatry at the University of Michigan. All psychometricians are directly supervised by an onsite Ph.D.-level neuropsychologist in Psychiatry; furthermore, [name], a clinical psychologist who is a co-investigator on this project will oversee all neuropsychological data collection and extraction. Components of the MACFIMS, include in this study are as follows:

Symbol Digit Modalities Test (SDMT): Consists of a series of 9 symbols paired with a single digit in a key at the top of an exam sheet. Below the key, the remainder of the page consists of pseudo-randomized sequence of these symbols, and the examinee must recall the correct corresponding digit as quickly as possible, either by scanning the key, or using recall. The final score consists of the total number of items correct within a 90 second testing interval. The **oral administration** will be used for this study. The Standard Form and Alternate Form of the SDMT will be used.

Paced auditory serial addition test (PASAT): Patients listen to a series of audiotaped digits and must add each consecutive digit to the one immediately preceding it. Digits presented at two different rates (every 2 seconds or 3 seconds). Scores reflect the total number of correct responses at each presentation rate (PASAT-2 or PASAT-3). Two alternate forms, Form A and Form B, will used in this study.

California Verbal Learning Test (CVLT-II): Subjects learn a 16-word list (list A), the recall of which is examined over a course of 5 trials. Subjects are then asked to recall a new 16-word list (interference list, List B), after which time the original list is reassessed after a 25-minute delay interval. Total number of words recalled on trials 1-5 and delayed recall are scored. The CVLT-II has both a Standard Form and an Alternative form that will be used in this study.

Brief Visuospatial Memory Test – Revised (BVMT-R): Assesses spatial learning and memory using a matrix of simple abstract designs presented in three trials (10 seconds each). Subjects are asked to recall (immediate and after a delay) and recognize the designs from distractor designs. Form 1 and Form 2 will be used in this trial.

Judgment of line orientation test (JLO): Measure of visual-spatial abilities. Subjects are required to identify the angle defined by 2 stimulus lines, from those which are located in a visual array of lines that cover 180 degrees. Scores reflect total number of correct responses. Form H and a Form V will be used in this study.

Controlled word association test (COWAT): Measure of phonemic fluency, in which subjects are asked to name as many words as they can that begin with 3 different stimulus letters within 60 seconds. Scores reflect total number of words generated across all 3 trials. Two alternate versions (CFL/PRW) of the COWAT will be used.

Nine-hole Peg Test (NHPT): Using a standard NHPT board, subjects place plastic pegs into 9 holes one at a time, and remove them one at a time as quickly as they can. Test is scored as

the time (seconds) it takes the subject to complete the task. Two trials on both dominant and non-dominant hands are completed.

Trail Making Test (Part A and B): Both parts of the Trail Making Test consist of 25 circles distributed over a sheet of paper. In Part A, the circles are numbered 1 – 25, and the patient should draw lines to connect the numbers in ascending order. In Part B, the circles include both numbers (1 – 13) and letters (A – L); as in Part A, the patient draws lines to connect the circles in an ascending pattern, but with the added task of alternating between the numbers and letters (i.e., 1-A-2-B-3-C, etc.). The patient should be instructed to connect the circles as quickly as possible, without lifting the pen or pencil from the paper. Time the patient as he or she connects the "trail." Results for both TMT A and B are reported as the number of seconds required to complete the task; therefore, higher scores reveal greater impairment.

The North American Adult Reading Test (NAART) - 35: The NAART is a widely used to estimate verbal intellectual ability/verbal intelligence. The test consists of a list of 35 irregularly pronounced English words. The examinee is required to read each word, and their score is based on the number of correctly pronounced words (according to American and Canadian pronunciation rules). Because scores on the NAART are thought to reflect basic aspects of crystallized intelligence and are not expected to change, this test will only be administered once – at baseline.

Go/No-go test: The GNG task involves the presentation of letter stimuli one at a time every 500 ms on the computer screen. After a brief training session, participants are instructed to quickly press a button each time they see the target letters X, Y or Z: either 1) each time the target letters are presented (go trials), or only when the target letters are presented in alternating non-repeating fashion (no-go trials). Reaction time and accuracy are recorded.

Two fixed batteries of these tests (see **table 2** below) will be created. Order of administration of Fixed Test Battery A and Fixed Test Battery B will be randomized across subjects.

Table 2: Cognitive batteries		
Test	Fixed Test Battery A	Fixed Test Battery B
SDMT	Standard Form	Alternate Form
PASAT 3	Form A	Form B
PASAT 2	Form A	Form B
CVLT-II	Standard Form	Alternate Form
BVMT-R	Form 1	Form 2
JLO	Form H	Form V
COWAT	CFL	PRW
NHPT	Standard administration	Standard Administration
Trails A and B	Standard form	Alternative form
NAART	Standard Form – baseline only	Standard form – baseline only
Go/No-go test	Standard administration	Standard administration

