2. STUDY OBJECTIVES AND ENDPOINTS

2.1 Objectives

The objectives of this randomized, rater-blinded clinical trial are to 1) determine the effects of OSA on specific domains of cognitive function in patients with MS; and 2) assess the effects of OSA treatment with positive airway pressure (PAP) therapy on cognitive dysfunction in MS patients.

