9.0 DATA ANALYSIS/STATISTICAL METHODS

9.1 Sample Size Determination

Estimates (means and standard deviations) are derived from our recent data that evaluated SDMT scores among MS subjects referred for overnight PSG, and previously published interventional studies in that evaluated the effects of medical interventions on components of the MACFIMS in MS patients. We have chosen to focus on SDMT score as the primary outcome variable of interest, as the SDMT encompasses multiple domains of cognitive function, is frequently used in MS clinical studies as a reliable measure of cognitive impairment, and is sensitive to changes in intervention.

Based on a power analysis of two sample means (unequal sample sizes, with 2:1 randomization) with a 0.05 two-sided significance level, and an estimated S.D. of 9, a total sample size of 140 subjects will have an 86.3% power to detect a 5-point difference in SDMT score between groups, on month 3 testing, for hypothesis 2. Similarly, using individual MACFIMS components as outcome variables (in separate models), a multiple linear regression power analysis shows that a sample size of n=140 subjects will yield 88% power to detect an R-square difference of 0.05 for the test predictor of interest (% PAP use per month, as a continuous measure), assuming the R-squared explained by the adjustment variables is at least 0.3.

Although we predict a low dropout rate due to the short duration of the study, if we assume a dropout rate of 15% (10 dropouts per group), we will still have a power of 81.2% power to detect a 5-point difference in SDMT score between groups, on month 3 testing.

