9.2 Analysis of Primary Endpoint

Aim 1: Multivariate linear regression models will be used to analyze the effects of baseline PSG-derived standard measures of sleep disordered breathing (including RDI, ODI, minimum O2 saturation), on individual cognitive test scores (continuous outcome variables of interest, in separate models) for Aim 1, controlling for other sleep, serological, and clinical variables. Additional models that use computed respiratory cycle-related EEG changes (calculated as the maximum difference between the mean EEG powers associated with each of the 4 respiratory cycle segments as predictor variables) will be used to evaluate the effects of respiratory-related cortical microarousals on cognitive test scores, controlling for other clinical and sleep-related variables. Separate models that use computed temporal patterns of sleep stages as predictors of cognitive test scores will also be constructed.

Aim 2: Multivariate linear regression models will be used to test the effects of Group effect on 3-month (“post”) cognitive test scores, controlling for baseline (“pre”) test scores. We will also examine the association of PAP use as a continuous variable, based on mean nightly hours of use per month, on 3-month individual cognitive test scores, controlling for baseline scores. Separate models will be used for each cognitive test of interest. Predictor variables that are unbalanced between groups despite randomization will be used as covariates in the analyses.

To evaluate early effects of PAP therapy on cognitive scores, sleep stage dynamics will also be assessed during PAP titrations to determine whether changes in sleep stage stability predict improvements on cognitive test scores in separate models.

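### The co-investigator who oversees all cognitive data collection and extraction belongs to a group declared unblinded, and no barrier to the raters or to the extraction step is stated

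*Combined protocol and SAP*

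**What the plan says.** Section 2.1 describes the trial as rater-blinded. Section 5.2 says who is masked: besides the PSG technicians and interpreters, "study staff who conduct and score neuropsychological tests will remain blinded to group allocation for the duration of the study". It then says who is not: "The subject, PI, co-investigators, coordinators, and statistician will not be blinded". Section 6.4 repeats both lists. Neither section makes an exception for any individual co-investigator.

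Section 6.2 describes how the cognitive data are produced. "All MACFIMS testing will be performed by blinded, trained psychometricians". On supervision it says "All psychometricians are directly supervised by an onsite Ph.D.-level neuropsychologist in Psychiatry", and it adds that "a clinical psychologist who is a co-investigator on this project will oversee all neuropsychological data collection and extraction".

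Section 7.1 makes cognitive performance the primary outcome measure, and Section 9.1 singles out the SDMT. For the Aim 2 comparison, Section 9.2 controls for the baseline score and adds: "Predictor variables that are unbalanced between groups despite randomization will be used as covariates in the analyses".

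**The concern.** Subjects know their arm. Group 2 defers PAP until after month 3 testing, and no sham is used. The design therefore leans heavily on keeping the handling of cognitive outcomes independent of allocation. The plan secures this for the people who administer and score the tests. It does not secure it for the co-investigator placed over the whole flow of cognitive data, who falls in a class that is allowed to know the arm.

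Extraction is the more exposed step. Blinding is promised for conducting and scoring; turning scored tests into analysis data is not covered by that promise, and it is one of the two things this co-investigator oversees. If knowledge of the arm influenced instructions to raters, or which results were carried forward and how, the primary comparison could move in either direction, and the plan names no step designed to prevent it.

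**Working it through.** No figure in the plan is at issue. The power calculation in Section 9.1 does not depend on who is blinded, so the check is a comparison of role lists.

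1. **Test administration.** Done by psychometricians, stated to be blinded (6.2, and 5.2 and 6.4 for those who conduct tests). Protected.
2. **Scoring.** Covered by the same sentence in 5.2 and 6.4, for the duration of the study. Protected.
3. **Direct supervision of the psychometricians.** An onsite neuropsychologist (6.2). This person's blinding status is not stated.
4. **Oversight of collection.** A co-investigator (6.2). Co-investigators are unblinded as a class (5.2, 6.4). Not protected.
5. **Oversight of extraction.** The same co-investigator. Extraction lies outside the wording on conducting and scoring, and the overseer is in the unblinded class. Not protected.
6. **Barrier between steps 4–5 and steps 1–2.** None is described in 5.2, 6.2, 6.4, 10 or 11.

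So the gap is at steps 4 to 6, with step 3 open. It follows from reading 6.2 against 5.2 and 6.4 and needs no inference beyond the class membership that 6.2 itself states. The documents do not say that this person will in fact be told allocations, only that nothing keeps them from this person.

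The **statistician** is a separate matter, at the analysis stage:

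- The statistician is unblinded (5.2, 6.4).
- The covariate rule in 9.2 depends on imbalance between groups. It gives no list of variables, no threshold and no deadline.
- Imbalance between groups cannot be assessed without the allocation. Withholding allocation while keeping this rule is therefore impossible.
- Coded arm labels would not help. With 2:1 randomization and about 93 against 47 subjects, the group sizes identify the arms.
- Hence masking is workable here only if the rule is replaced by covariates fixed in advance.

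**The case against.** The strongest reply is that the protocol does what its label says. "The objectives of this randomized, rater-blinded clinical trial are to" is a statement about raters, and the raters are blinded. A reader might infer from the co-investigator's role that the rater-blinded claim is undercut. The documents do not support that: a co-investigator who scored tests would be breaching 5.2 and 6.4, and an unblinded statistician has no bearing on the blinding of raters. This part of the reply stands in full.

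A reader might also infer that decisions on test validity or scoring queries pass through someone who knows the arm. The text says only that the co-investigator oversees, and it describes no such adjudication or power to override a score. Direct supervision belongs to someone else. This also stands.

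Third, there are other restraints. The SDMT is a count of correct items in 90 seconds, the peg and trail-making tests are timed, and the Go/No-go task runs on a computer. The order of the two batteries is randomized. Section 11.1 requires CRF entries to be verifiable against source documents unless the CRF is itself the source, and Section 10.2 provides for a monitor. These limit how far a blindly scored result could be altered at extraction. They do not blind the overseer, so they reduce the concern without closing it.

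Finally, it might be inferred that the statistician is documented as the person who selects covariates. Section 9.2 names nobody. It is a reasonable guess, but no more than that.

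**Conclusion.** The point holds in a limited form. The people who conduct and score the cognitive tests are blinded and the rater-blinded label is sound. The co-investigator over all cognitive data collection and extraction belongs to a class declared unblinded, and nothing separates that person from the raters or from the extraction step. In an open-label trial without a sham this is an avoidable route for bias in the primary outcome.

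Its size cannot be estimated. The documents give no basis for assuming a shift of any particular number of SDMT points, and blinded scoring of standardized tests keeps the opportunity small. The conclusion assumes that the unblinded list in 5.2 and 6.4 means what it says for every co-investigator. If practice already separates these roles, only the wording is deficient.

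The unblinded statistician combined with an imbalance-driven covariate rule is a secondary weakness with its own mechanism and its own remedy. It should not be counted as evidence against rater blinding.

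**What to change.** Amend Sections 5.2 and 6.4 in one of two ways:

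- state that the co-investigator overseeing neuropsychological data has no access to allocation until the cognitive data are locked; or
- state that unblinded co-investigators have no role in collecting, scoring or extracting cognitive data, and change 6.2 to match.

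The same amendment should give the blinding status of the onsite supervising neuropsychologist.

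The cost is protocol wording and control of access to the allocation list, with no added visits. The small downside is that other team members must handle contacts that would reveal the arm. Section 10.1 assigns one such duty, telephoning participants in severe distress, to a psychologist co-investigator. Names are removed from the public copy, so whether this is the same person cannot be told; the sponsor should check.

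Separately, in Section 9.2, replace the imbalance rule with a covariate set fixed before allocation is linked to outcomes, for example the baseline score and the randomization stratum (RDI below 30, or 30 and above). Once that is done, allocation can be withheld from the statistician until the analysis programs are final. The cost is giving up adjustment for imbalances noticed afterwards in the main model; these could still be examined in a labelled sensitivity analysis.

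### Aim 1 pools baseline scores from two test forms for most of the battery without naming a form term, which costs some precision but does not cause bias

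*Combined protocol and SAP*

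**What the plan says.** Section 6.2 randomizes which battery a subject takes first: "Order of administration of Fixed Test Battery A and Fixed Test Battery B will be randomized across subjects". The test descriptions and Table 2 in that section show which tests differ between batteries.

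- **Two forms:** SDMT ("The Standard Form and Alternate Form of the SDMT will be used"), CVLT-II ("The CVLT-II has both a Standard Form and an Alternative form that will be used in this study"), PASAT-2 and PASAT-3, BVMT-R, JLO, COWAT, and Trails A and B.
- **Same in both batteries:** NHPT ("Using a standard NHPT board"), NAART ("this test will only be administered once – at baseline") and Go/No-go ("Standard administration" under both batteries in Table 2).

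Section 9.2 fits linear regressions of the sleep-study measures "on individual cognitive test scores (continuous outcome variables of interest, in separate models) for Aim 1", and describes the adjustment as "controlling for other sleep, serological, and clinical variables". It lists no individual covariates. Neither section mentions form, battery or order as a model term, and neither describes equating of forms or form-specific norms.

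**The concern.** Aim 1 is cross-sectional, with one baseline score per subject. If one form of a test is harder than the other, two equally able subjects get different scores according to the battery they happened to draw. A model without a form term treats that difference as unexplained noise. The estimates for RDI, ODI and minimum oxygen saturation then have wider intervals than the design requires. The affected tests include the SDMT, which section 9.1 names as the primary outcome variable of interest, and Aim 1 is one of the two primary endpoints in section 2.2.1. The source of this noise is a factor that the trial itself randomizes, so it can be removed at almost no cost.

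**Working it through.** **Inputs from the documents.** About 175 subjects for Aim 1 (section 4.0). From section 9.1: two-sided 0.05, SDMT standard deviation 9, R-square of adjustment variables at least 0.3, and an R-square increment of 0.05. That increment is stated for PAP use in Aim 2. The plan gives no power figure for Aim 1.

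**Assumptions.** Batteries A and B are equally frequent at baseline (the ratio is not stated). The form difference d, in within-form SD units, is shown as a range because the documents do not give it. An increment of 0.03 is added as a smaller effect. Five adjusters are assumed; ten change no power figure by more than about 0.02 points.

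**The plan's own figures first.** For a 5-point SDMT difference with SD 9 and groups of 93 and 47, the noncentral t gives 86.9% against the stated 86.3%. For the regression at n = 140, f² = 0.05/(1 − 0.30 − 0.05) = 0.0769. Power is 88.1% with ten adjusters and a noncentrality based on the error degrees of freedom, and 90.3% with n × f², against the stated 88%. Neither figure depends on the form question.

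**Added variance.** An omitted randomized two-level factor with share p and mean difference d adds p(1 − p)d² to the residual variance, which is d²/4 at p = 1/2. With outcome variance 1 within form, the residual variance is 1 − 0.30 − increment: 0.67 for 0.03 and 0.65 for 0.05.

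**Standard error ratio**, without against with the form term: √(1 + (d²/4)/residual variance). Example at d = 0.5, increment 0.03: √(1 + 0.0625/0.67) = 1.046.

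**Power.** Noncentral F with 1 numerator degree of freedom and λ = 175 × increment/(residual variance + d²/4). Example at increment 0.03: λ = 5.25/0.67 = 7.84 with the term, and 5.25/0.7325 = 7.17 without it at d = 0.5.

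| d (SD) | SDMT points (9 × d) | SE increase, increment 0.03 / 0.05 | Power, increment 0.03 | Power, increment 0.05 |
|---|---|---|---|---|
| form term included | – | – | 79.5% | 95.4% |
| 0.2 | 1.8 | 0.7% / 0.8% | 78.9% | 95.2% |
| 0.3 | 2.7 | 1.7% / 1.7% | 78.2% | 94.8% |
| 0.5 | 4.5 | 4.6% / 4.7% | 75.9% | 93.6% |
| 0.7 | 6.3 | 8.8% / 9.0% | 72.5% | 91.7% |

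**Bias check.** In 4,000 simulated trials of 175 subjects with a true slope of −2.01 (−√(0.05 × 81)) and no form term, the mean slope was −2.01 for a 3-point form difference and −2.02 for a 5-point difference. The empirical standard errors without and with the form term were 0.573 and 0.562 (3 points), and 0.588 and 0.555 (5 points). These are increases of 2.0% and 5.9%, in line with the formula.

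**The case against.** The strongest reply is that randomizing the order already does the essential work. Form is independent of apnea severity in expectation, no stated figure is missed, and alternate forms may be close to equivalent. This largely stands, and it is why the point is minor. At d = 0.2 or less the loss is under one percentage point of power. Nothing in the documents suggests a difference as large as 0.7 SD, which on the SDMT would exceed the 5 points for which Aim 2 is powered.

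A reader might infer more than the documents support, in five ways.

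- **Every Aim 1 estimate is affected.** It is not: three tests are identical in both batteries.
- **The apnea coefficients are biased, or chance imbalance of form across severity is a further harm.** Chance imbalance is the route by which the omitted factor adds variance, so it is already in the standard error and must not be counted twice.
- **The plan rules a form term out.** Section 9.2 gives classes of covariates, not a closed list. Form does not fall naturally into any of those classes, but it is unspecified rather than excluded.
- **The battery taken is already recorded.** This is a fair inference from a randomized order, but no section says it.
- **Aim 2 escapes because its models adjust for the baseline score.** With the order randomized, a subject's other score is on the opposite form. Adjusting for it does not absorb the form difference and, with a positive slope on baseline, enlarges the contrast.

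What survives is that randomization prevents bias but does not remove the added variance, whereas a covariate does.

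**Conclusion.** The point holds as a small, optional gain in precision for the Aim 1 models of the two-form tests. The loss ranges from negligible to modest: 0.6 to 7.0 percentage points of power at an R-square increment of 0.03, and 0.2 to 3.7 points at 0.05, for form differences of 0.2 to 0.7 SD. At 0.05 power stays above 90% throughout. These sizes rest on an assumed form difference, an equal split of batteries, 175 analysed subjects and adjusters at R-square 0.30. The finding that the Aim 1 text names no form term rests on the documents alone. The validity of Aim 1 is not in question.

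**What to change.** In section 9.2, Aim 1, state that each model for a test with alternate forms (SDMT, PASAT-2, PASAT-3, CVLT-II, BVMT-R, JLO, COWAT, Trails) includes an indicator for the battery, A or B, taken at baseline. State also that the battery given is recorded for each subject. The models for NHPT, NAART and Go/No-go need no such term. The cost is a short addition to the text, one data field if the battery is not already captured, and one degree of freedom per affected model out of about 175 subjects.
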